#### 6.3.4 ***Risk assessment with regards to the Covid-19 pandemic:***

Current recommendations from the Public Health Agency of Sweden (Folkhälsomyndigheten) and other authorities will be considered on a day-to-day basis. Assessment sessions with Sponsors, Investigators and CRO/vendor representative members to align on local restrictions, impact assessment, contingency plans and study-specific risk mitigation strategies will be made to safeguard the study conduct and the safety of the patients included in the study. Risks regarding patient safety, study performance and data quality/integrity will be assessed on an ongoing basis during the study. Any identified risks and mitigating actions will be documented in a risk log as part of the Sponsor's trial master file (TMF).

EMAs Guidance on the Management of Clinical Trials during the Covid-19 (Coronavirus) pandemic as well as local guidelines from the Swedish Medical Products Agency will be taken into consideration.

### **7 STUDY OBJECTIVES AND ENDPOINTS**

#### **7.1 Primary objective**

To evaluate the safety and tolerability of NLX-112, titrated up to a maximum of 2 mg/day, compared to placebo during 8 weeks of daily treatment in PD patients with LID.

##### **7.1.1 *Primary endpoints***

- Frequency, intensity and seriousness of AEs
- Clinically significant changes from baseline in:
  - ECG
  - Vital signs
  - Safety laboratory parameters
  - Physical examinations
- Suicidal ideation/behavior as assessed by the Columbia Suicide Severity Rating Scale (C-SSRS).

#### **7.2 Secondary objective**

To assess the preliminary efficacy of NLX-112 treatment in reducing troublesome LID.

##### **7.2.1 *Secondary endpoints***

- Change from baseline at the final efficacy clinic visit (Day 42) in the Unified Dyskinesia Rating Scale (UDysRS) total score [Timeframe: Baseline to Day 42]. Patients will be challenged with 150% of their standard L-DOPA dose (maximum L-DOPA dose 250 mg) 30 minutes prior to the first UDysRS assessment.

- Change from baseline in UDysRS total score at Day 28, after a 150% L-DOPA dose challenge.
- Change from baseline in total objective score (Parts III, IV) of the UDysRS at Day 28 and Day 42, after a 150% L-DOPA dose challenge.
- Change from baseline in ON Time Without Troublesome Dyskinesia (ON Without Dyskinesia plus ON With Non-troublesome Dyskinesia) based on a PD Home Dyskinesia Diary.
- Change from baseline in Unified Parkinson's Disease Rating Scale (UPDRS) scores (Part III, motor examination).
- Change from baseline in UPDRS combined scores (Parts I, II, III and IV).
- Clinical Global Impression of Change (CGI-C) in overall PD symptoms
- Change from baseline in dyskinesia scores measured by the Kinesia 360 (Great Lakes Neurotechnologies, Inc) wearable dyskinesia assessment system.

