## 6.2 Study rationale

L-DOPA (levodopa, L-3,4-dihydroxyphenylalanine) is the gold-standard pharmacotherapy for PD. L-DOPA is converted to DA primarily in dopaminergic neurons and, given that motor symptoms of PD are caused by a lack of DA, L-DOPA decreases the severity of these symptoms. However, after several years of treatment, use of L-DOPA often leads to fluctuations in therapeutic efficacy (ON and OFF periods) and to induction of dyskinesia which can be serious and disabling. Dyskinesias are AIMs that interfere with normal movements and can occur even at rest. Since dyskinesias are induced by L-DOPA, they are often referred to as L-DOPA-induced dyskinesia, or LID [1, 2].

LID is poorly treated, with few options available to the treating neurologist or physician. Some LID patients respond to amantadine, although tolerability and efficacy are limited. Alternatively, physicians lower the daily doses of L-DOPA or reduce administration intervals and L-DOPA doses to avoid peak-dose LID. However, this may increase periods of OFF and increase parkinsonism in PD patients [1, 3, 4]. LID has been shown to reduce the patient's quality of life (QOL), as well as to increase the risk of falls and health care costs. LID has been shown to worsen the activities of daily living (ADL), and patients report that their dyskinesia negatively impacts walking and balance, public and social settings, exciting or emotional settings, doing hobbies and other activities, handwriting, and dressing [5, 6].

Although Parkinson's disease is strongly associated with dysfunction of the dopaminergic system, serotonin (5-hydroxytryptamine, 5-HT) levels are also reduced in the brain of PD patients, as shown in post-mortem analyses. The dyskinesia observed in PD patients receiving L-DOPA is due to the fact that serotonergic neurons can take up L-DOPA and convert it to DA (similarly to dopaminergic neurons), but in a dysregulated manner as a 'false neurotransmitter' [7-9]. Hence, experiments in animal models as well as brain imaging studies in human PD-LID patients show that when serotonergic neurons are inhibited, the dyskinesia induced by L-DOPA is markedly reduced. These results and others indicate that inhibition of

5-HT neurons using drugs such as NLX-112, which is an agonist at inhibitory 5-HT1A somatodendritic autoreceptors, is a promising strategy to treat LID in PD patients [10-13].

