### 9.4 Inclusion criteria

To be eligible to participate in the study, a patient must meet ALL of the following inclusion criteria:

1. Patient is 30 – 85 years old (inclusive) with a diagnosis of idiopathic PD according to the UK Parkinson's Disease Society Brain Bank Clinical Diagnosis criteria.
2. PD patient is stably and optimally treated with L-DOPA; other anti-PD treatments are allowed if used for at least 4 weeks of previous continuous treatment.
3. Patient agrees to be challenged with 150% of their normal L-DOPA dose (maximum L-DOPA dose 250 mg) 30 minutes prior to efficacy assessments at baseline (Visit 2) and at the 2 efficacy clinic visits (Visits 6 and 7).

4. PD patient exhibits troublesome peak-dose LID, confirmed by a score of at least 1 on part IV, item 33 (disability) of the UPDRS at screening (Visit 1) and at Day 1 (baseline, Visit 2).
5. At least 90 minutes in total for each 24-hour period during 2 days are indicated as “ON with troublesome dyskinesia” (according to the PD Home Dyskinesia Diary) prior to Day 1 (baseline, Visit 2).
6. Patient (and/or caregiver) demonstrates ability to accurately complete the PD Home Dyskinesia Diary entries during the screening visit.
7. Patient can read well enough to understand the informed consent document and other subject materials.
8. Female patients of child-bearing potential must have a negative urine pregnancy test at screening (Visit 1) and on Day 1 (Visit 2), must agree to avoid pregnancy during the study, and must practice abstinence (only allowed when this is the preferred and usual lifestyle of the subject) or must agree to use a highly effective method of contraception with a failure rate of < 1% to prevent pregnancy (combined [oestrogen and progestogen containing] hormonal contraception associated with inhibition of ovulation [oral, intravaginal, transdermal], progestogen-only hormonal contraception associated with inhibition of ovulation [oral, injectable, implantable], intrauterine device [IUD] or intrauterine hormone-releasing system [IUS]) starting from 4 weeks prior to administration of the study drug and continuing during the course of the study until 4 weeks after last after IMP administration. Female subjects must agree to refrain from donating eggs from the date of dosing until 3 months after dosing with the IMP. Their male partner must agree to use a condom during the same time frame if he has not undergone vasectomy.

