### 11.3.3 ***PD Home Dyskinesia Diary***

A PD Home Dyskinesia Diary (electronic) will be completed by the patients and/or caregiver with concordance in ON time with dyskinesia between study staff and patient. The diary is integrated in the Kinesia 360 wearable dyskinesia assessment system (Section 11.3.6) and is based on the PD Home Diary developed by Hauser et al 2004 [26]. The diary will be used to score 5 different conditions in 30-minute time intervals during 2x24 hours prior to Visit 2, Visit 6 and Visit 7:

- ASLEEP;
- OFF;
- ON (i.e., adequate control of PD symptoms) without dyskinesia;
- ON with non-troublesome dyskinesia;
- ON with troublesome dyskinesia.

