### **9.2.3      ON Time Without Troublesome Dyskinesia**

Change from baseline in ON Time Without Troublesome Dyskinesia (ON Without Dyskinesia plus ON With Non-troublesome Dyskinesia) based on a PD Home Dyskinesia Diary will be summarized using descriptive statistics for all assessment time points. In this analysis, the number of records of ON Without Dyskinesia plus ON With Non-troublesome Dyskinesia divided by the number of non-missing awake records (sleeping records are excluded) for all measurements prior to Visit 2 and for all measurements from 4\*24 hours prior to and up until Visit 6 and 7 respectively will be used as input data for each patient respectively. If there is not

at least 8 hours recorded data available for each patient and visit window, the corresponding timepoint is set to missing for the patient. ON Time Without Troublesome Dyskinesia will be analysed using inferential statistics as described under 9.2.1 above.

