**Table ON 1 ON Time Without Troublesome Dyskinesia (Full analysis set)**

Use the same format as for Table UD 1. Add a footnote stating that the sum of records of ON Without Dyskinesia plus ON With Non-troublesome Dyskinesia for the 2\*24 hours measurements prior to each visit has been used as input data for each patient respectively. Produce the table above for PPS as well, providing there is any de facto difference between the analysis sets. If the LMM is performed using transformed data, insert a footnote about this as well. If the LMM approach is dropped in favour of non-parametric tests, update the table and footnotes accordingly.

*10.2.3.3 Unified Parkinson's Disease Rating Scale (UPDRS)*

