#### 16.2.6 Individual Efficacy Response Data

- Listing 16.2.6- 1 UDysRS (Full analysis set)
- Listing 16.2.6- 2 UPDRS, parts I-IV (Full analysis set)
- Listing 16.2.6- 3 CGI-S, CGI-C (Full analysis set)
- Listing 16.2.6- 4 KPPS (Full analysis set)
- Listing 16.2.6- 5 PDQ39 (Full analysis set)
- Listing 16.2.6- 6 HADS (Full analysis set)
- Listing 16.2.6- 7 ICIQ-OAB (Full analysis set)
- Listing 16.2.6- 8 ESS (Full analysis set)
- Listing 16.2.6- 9 Kinesia 360 wearable device data (Full analysis set)
- Listing 16.2.6- 10 PD Home Dyskinesia Diary (Full analysis set)

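### The only analysed diary endpoint combines OFF time and troublesome dyskinesia in its complement; add troublesome time as an analysed share and show OFF share beside it.

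*Protocol*

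**What the plan says.** Protocol Section 7.2 gives the secondary objective: "To assess the preliminary efficacy of NLX-112 treatment in reducing troublesome LID". Inclusion criterion 5 (Section 9.4) selects patients on the matching diary state, ON with troublesome dyskinesia: "At least 90 minutes in total for each 24-hour period during 2 days are indicated as". Section 11.3.3 describes the instrument, with the seventh visit as the last of three time points: "The diary will be used to score 5 different conditions in 30-minute time intervals during 2x24 hours prior to Visit 2, Visit 6 and Visit". The five states are asleep, OFF, and ON with no, non-troublesome or troublesome dyskinesia.

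The only diary endpoint, in Section 7.2.1, is "Change from baseline in ON Time Without Troublesome Dyskinesia (ON Without Dyskinesia plus ON With Non-troublesome Dyskinesia) based on a PD Home Dyskinesia Diary". The protocol gives it no denominator. SAP 9.2.3 does: the two good ON states are added and "divided by the number of non-missing awake records (sleeping records are excluded"). All records before Visit 2 are used, and those from up to 4\*24 hours before Visits 6 and 7. A visit window needs at least 8 hours of data, and the model is that of SAP 9.2.1.

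Table ON 1 is the only diary table in the SAP. Its footnote describes something different, a sum of records "for the 2\*24 hours measurements prior to each visit has been used as input data for each patient respectively". The only other planned diary output is an individual listing, "PD Home Dyskinesia Diary (Full analysis set"). No table or test covers troublesome time or OFF time.

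**The concern.** Patients are selected on troublesome time and the objective is to reduce troublesome dyskinesia, yet that diary state is neither summarised nor tested by arm. It enters the analysis only mixed with OFF, inside the complement of the endpoint.

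A rise in the endpoint could be taken as an antidyskinetic effect when OFF had fallen. A flat result could be taken as no effect when troublesome time had fallen and OFF had risen. Protocol Section 8.3 says the study is to support the design of further PD-LID studies, and for that purpose it matters which component moved.

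OFF is a relevant component in this disease. On lowering or fractionating L-DOPA to control dyskinesia, Protocol Section 6.2 says: "However, this may increase periods of OFF and increase parkinsonism in PD patients". The same section reports anti-parkinsonian activity of NLX-112 itself in marmosets. If that carried over to patients, it could reduce OFF.

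**Working it through.** The documents give no effect size, SD or baseline for any diary state, so there is no planned figure to reproduce. The check is an accounting identity followed by scenarios.

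**Identity.** Within non-missing awake records (SAP 9.2.3, states from Protocol 11.3.3):

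OFF + ON without + ON non-troublesome + ON troublesome = awake

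Endpoint = (ON without + ON non-troublesome) / awake = 1 − OFF/awake − ON troublesome/awake

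This is exact for each patient and visit and needs no assumed values. It depends on the awake denominator. If the endpoint is read as hours, or as the sum of records in the Table ON 1 footnote, the complement of 24 hours also contains sleep.

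**Scenarios.** Assumed, not from the documents: 16 awake hours; baseline OFF 4 h, troublesome 2 h, non-troublesome 4 h, ON without dyskinesia 6 h. Good ON is 4 + 6 = 10 h and the endpoint is 10/16 = 62.5%. A shift of 1.5 h is 1.5/16 = 9.4 points.

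| Scenario | OFF (h) | Troublesome (h) | Good ON (h) | Endpoint | Change in endpoint (points) | Change in troublesome share | Change in OFF share |
|---|---|---|---|---|---|---|---|
| Baseline | 4.0 | 2.0 | 10.0 | 62.5% | | | |
| A. Troublesome −1.5 h | 4.0 | 0.5 | 11.5 | 71.9% | +9.4 | −9.4 | 0 |
| B. OFF −1.5 h | 2.5 | 2.0 | 11.5 | 71.9% | +9.4 | 0 | −9.4 |
| C. Troublesome −1.5 h, OFF +1.5 h | 5.5 | 0.5 | 10.0 | 62.5% | 0 | −9.4 | +9.4 |
| D. Troublesome +1.5 h, OFF −3 h | 1.0 | 3.5 | 11.5 | 71.9% | +9.4 | +9.4 | −18.8 |

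The endpoint is identical in A, B and D, although troublesome time falls, stays put and rises respectively. In C it does not move. The last two columns separate all four.

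**Range.** At 14 awake hours, A, B and D each give 9.5/14 − 8/14 = +10.7 points. At 18 hours they give 13.5/18 − 12/18 = +8.3 points. C gives 0 in both.

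**Entry minimum.** A patient with exactly 90 minutes of troublesome time has 1.5/18 = 8.3% to 1.5/14 = 10.7% of awake time in that state. Abolishing it can raise the endpoint by at most that much. The entry criteria set no limit on OFF time.

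**Other planned measures, compared with daily time in the troublesome or OFF state:**

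- UDysRS (Protocol 11.3.1 and 11.3.2): Parts III and IV are rated in clinic after a 150% L-DOPA challenge. Parts I and II record perceived impact on daily living, not hours.
- Kinesia 360 (SAP 9.2.6): the variable Dyskinesia detect is a home measure of dyskinesia, not described as grading troublesomeness or identifying OFF.
- UPDRS (Protocol 8.2 and 11.3.4, SAP 9.2.4): Part III is rated in ON after the challenge. Part II, and Part IV with its time spent with dyskinesia, are tested only within the combined score.
- CGI-C (SAP 9.2.5): overall PD symptoms.
- Adverse events (Protocol 11.2.1.1): worsening of dyskinesia outside the challenge, or of PD symptoms, is reported, but not as time.

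**The case against.** The strongest defence is that the endpoint works as a net-benefit measure should. Staying flat when dyskinetic time turns into OFF means it does not credit a bad exchange. Efficacy is secondary, the tests are exploratory, and SAP 5.1 calls significant findings indicative rather than confirmatory. Individual diary data are listed in any case. All of this stands, and it limits the consequence. It does not supply the missing decomposition: a listing gives neither an arm-level estimate nor an interval.

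A reader might infer three stronger things that the documents do not support.

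- That the protocol expects OFF to rise on NLX-112. The Section 6.2 sentence on OFF concerns reducing L-DOPA, and the remark on older serotonergic compounds concerns other drugs. For NLX-112, Sections 6.1.1 and 6.2 report no impairment of L-DOPA's therapeutic-like actions in the animal models. The marmoset finding is weak support for a fall in OFF, not a rise.
- That a loss of L-DOPA benefit would go unseen. The UPDRS, CGI-C and adverse event reporting all give it some route to detection, and the UDysRS and Kinesia 360 address dyskinesia directly.
- That the endpoint is invalid and should be replaced. It should stay.

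It is also fair to object that the scenario hours are assumed. They show what can happen, not how likely it is. Since the three shares sum to one, a formal test of OFF as well as troublesome time would add little.

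**Conclusion.** The gap is a missing decomposition, not a wrong endpoint. As defined in SAP 9.2.3, the diary result cannot be attributed to troublesome dyskinesia or to OFF, and no other planned analysis gives daily time in either state. The identity is exact given the awake denominator. The sizes (8.3 to 10.7 points for a 1.5 h shift over 14 to 18 awake hours, and 0 for an exchange between the two states) rest on assumed hours. The consequence is moderate: no planned analysis is incorrect and efficacy is preliminary, but the diary's direct answer to the secondary objective is left unanalysed although the data are in hand.

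**What to change.** 1. Keep the existing endpoint. In SAP 9.2.3 and Table ON 1, add change from baseline in ON time with troublesome dyskinesia as a share of non-missing awake records, using the same windows, 8-hour rule and SAP 9.2.1 model.
2. Show change in OFF share alongside it descriptively, with an estimate and confidence interval and no further test. Unadjusted mean changes in the three shares sum to zero in the same patients, but the OFF interval cannot be obtained by subtraction, so it should be printed.
3. State that the diary result is interpreted together with the direction and confidence interval of the troublesome-time estimate, not through a significance gate. Table ON 1 follows the Table UD 1 layout, which prints p-values but no intervals, and SAP 9.2.1 produces the between-arm difference only after a significant treatment-by-visit test. The estimate and interval should therefore be shown whatever that test gives.
4. Align the Table ON 1 footnote (sum of records over 2\*24 hours) with SAP 9.2.3 (proportion, over up to 4\*24 hours before Visits 6 and 7).

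This should be specified before unblinding; otherwise it should be labelled post hoc. The cost is a few table rows from data already collected and one more endpoint tested without multiplicity adjustment.

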### 7.3 Exploratory objectives

- To assess the preliminary efficacy of NLX-112 treatment in improving selected non-motor symptoms of PD, including pain, bladder function, sleep function, mood and quality of living with PD.
- To collect blood samples for potential NLX-112 plasma concentration analysis.

#### 7.3.1 *Exploratory endpoints*

- Change from baseline in the King's Parkinson's Disease Pain Scale (KPPS) total score and in each of the 7 pain domain sub-scores.
- Change from baseline in the Parkinson's Disease Questionnaire (PDQ39) total score and domain scores.
- Change from baseline in the Hospital Anxiety Depression Scale (HADS)
- Change from baseline in the International Consultation on Incontinence Questionnaire (ICIQ) Overactive Bladder Module (ICIQ-OAB) total score.
- Change from baseline in the Epworth Sleepiness Scale (ESS).
- Plasma concentrations of NLX-112.

The NLX-112 plasma concentration analysis may only be performed if the Sponsor deems it necessary to answer any questions regarding compliance. The outcome of the results may not be reported in the clinical study report (CSR).

## 8 STUDY DESIGN

### 8.1 Overall study design and schedule of events

This is a two-arm, double-blind, randomized, placebo-controlled Phase 2a study evaluating the safety, tolerability, and preliminary efficacy of up to 2 mg/day of NLX-112 versus placebo in patients with moderate to severe L-DOPA induced dyskinesia (LID) in Parkinson's disease (PD). NLX-112 will be up-titrated to either 2 mg/day (1 mg BID) or to the highest well-tolerated dose less than 2 mg/day over 4 weeks, maintained at the well-tolerated dose for an additional 2 weeks, and then down-titrated over 2 weeks. An overview of the study design is shown in Figure 1.

Patients will report to the study clinic for a screening visit (Visit 1), followed by a baseline visit on Day 1 (Visit 2) where patients will be randomized and begin treatment. Two remote safety visits over telephone (Days 7 and 49 [Visit 3 and Visit 8]) will be conducted. Once treatment has commenced, there will be 2 in-person safety visits to the clinic (Days 14 and 21 [Visit 4 and Visit 5]), 2 in-person efficacy visits to the clinic (Days 28 and 42 [Visit 6 and Visit 7]) and one follow-up in-person final safety visit (Day 70 [Visit 9]). In total, patients will report to the clinic for 7 in-person visits. Patients entering the study will be randomized in a 2:1 ratio (16:8 patients) to receive either NLX-112 or placebo.

[figure not shown]
At Visits 2, 6 and 7, efficacy assessments will start 30 minutes after the patient has taken 150% of his or her regular L-DOPA dose, when the patient is ON and experiencing typical dyskinesia.

The order of assessments at each visit is specified in Section 8.2.

A PD Home Dyskinesia Diary (electronic) will be completed by the patients and/or caregiver with concordance in ON time with dyskinesia between study staff and patient. Two consecutive 24-hour diaries will be completed prior to randomization (baseline, Visit 2) and prior to the clinic visits on Days 28 and 42 (Visits 6 and 7).

A wearable dyskinesia assessment device will be used to monitor dyskinesias during a 2-day period prior to the baseline visit (Day 1, Visit 2) and a 2-day period prior to the clinic visits on Days 28 and 42 (Visits 6 and 7, respectively).

Blood will be collected for possible NLX-112 plasma concentration measurements on Days 14, 21, 28, 42 and 70 (Visits 4, 5, 6, 7 and 9).

**Figure 1** Overview of study design

AEs=adverse events, CGI-C=Clinical Global Impression of Change, ConMeds=Concomitant medications, C-SSRS=Columbia Suicide Severity Rating Scale, ECG=electrocardiogram, ESS=the Epworth Sleepiness Scale, HADS=the Hospital Anxiety Depression Scale, ICIQ-OAB=the International Consultation on Incontinence Questionnaire Overactive Bladder Module, KPPS=the King's Parkinson's disease Pain Scale, MMSE=Mini Mental Status Exam, UPDRS= the Unified Parkinson's Disease Rating Scale, PDQ39=the Parkinson's disease Quality of Life Scale (39-item), UDysRS=the Unified Dyskinesia Rating Scale.

CONFIDENTIAL

Patients will self-administer NLX-112 or placebo 2 times each day, once in the morning and once in the evening. Tablets should be taken with approximately 240 mL water during a meal. Active tablets will contain 0.25 mg NLX-112. Dose escalation will be as follows:

